**Sponsor/Quotient Sciences Confidential**

---

Any participant who withdraws from the study due to an AE will be followed up until the outcome is determined and written reports are provided by the investigator.

#### **14.4 Serious Adverse Events**

##### **14.4.1 Definition of Serious Adverse Events**

A serious adverse event (SAE) is defined as any untoward medical occurrence that at any dose:

- Results in death
- Is life-threatening
- Requires hospitalisation or prolongation of existing hospitalisation
- Results in persistent or significant disability or incapacity
- Consists of a congenital anomaly or birth defect
- An important medical event as recognised by the investigator

SAEs must be immediately reported to the sponsor.

Spontaneously reported SAEs will be collected until 30 days following the final study visit. SAEs experienced after this 30-day period will only be reported if the investigator suspects a causal relationship with the study drug.

##### **14.4.2 Definition of Suspected Unexpected Serious Adverse Reactions**

Suspected unexpected serious adverse reactions (SUSARs) are AEs that are believed to be related to an IMP and are both unexpected (i.e. the nature or severity is not expected from the information provided in the IB) and serious. SUSARs are subject to expedited reporting to the MHRA and EC (see [Section 16.3.2](#) for details on reporting SUSARs).

##### **14.4.3 Expectedness (Reference Safety Information)**

The Reference Safety Information is used for the assessment of the expectedness of all 'suspected' serious adverse reactions (SARs) that occur in clinical trials. The expectedness of a SAR is determined by the sponsor. The list of 'expected SARs' should be based on 'suspected' SARs that were previously observed and not on the basis of what might be anticipated from the pharmacological properties of a medicinal product or the compound class. An 'expected' SAR is therefore one that is listed in the Reference Safety Information. An adverse reaction, the nature of which is not consistent with the applicable reference safety information (in the IB for drugs in clinical development or SmPC for marketed drugs) is unexpected. Reports which add significant information on the specificity, increase in the occurrence or severity of a known and already documented SAR are unexpected events.

#### **14.5 Laboratory Measurements**

Venous blood and urine samples will be collected from the participants by a trained member of the clinical team. Consent will be collected from the participants for use of these samples for the purposes of the proposed study.

Blood and urine samples are sent for laboratory testing in linked anonymised form (participant number, gender and date of birth for analytical reasons). This information is able to be linked directly to the volunteer by the Quotient research team and study monitor; however, not by the laboratory staff or sponsor.

**Sponsor/Quotient Sciences Confidential**

---

Safety laboratory tests and virology will be carried out on blood samples, and drugs of abuse tests and urinalysis will be carried out on urine samples. Blood samples will be collected for DNA analysis, as detailed in [Section 14.5.9](#).

Blood and urine samples results will be reviewed by a physician and acted upon before the participant is dosed or receives their next dose, or is released from the study, as is appropriate. A list of the laboratory parameters measured is presented in [Appendix 1](#).

#### **14.5.1 Haematology, Clinical Chemistry and Coagulation**

Laboratory tests will be performed by The Doctors Laboratory according to the time schedules presented in [Appendix 5](#), [Appendix 6](#) and [Appendix 7](#). Blood samples will be collected and processed as detailed in the CSPM. Scheduled blood samples will be taken following an 8 h fast.

The acceptable deviations from the nominal blood sampling time points for laboratory assessments are:

- Post-dose/post-first dose blood samples will be taken  $\pm$  1 h from the nominal blood sampling time
- End of Study blood samples will be taken  $\pm$  1 day from the nominal blood sampling time

Creatinine clearance (CLcr) will be calculated at admission by The Doctors Laboratory using the Cockcroft-Gault equation [\[10\]](#) and body weight. Results of this assessment will be used for PK analysis and PK-PD modelling (reported separately).

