**8.3 Participant Withdrawal**

If a participant wishes to leave the study at any time, they will be permitted to do so. Every reasonable effort will be made by Quotient to complete final assessments/discharge procedures. Quotient will advise the sponsor of the withdrawal of any participant from the study.

Early withdrawal is defined as the date of the decision to withdraw the participant from the study. Participant completion is defined as the date of the last procedure conducted or last contact (e.g. discharge from the study or unscheduled visit) for that participant.

If a participant requests to leave the clinical unit earlier than the planned discharge time e.g. due to unforeseen personal circumstances, but aims to return to the clinical unit to complete the study, this will be documented as a participant self-discharge and a protocol deviation. The participant must complete the planned assessments/discharge procedures before discharge from the clinical unit, and may return for the next study period/assessments, as planned following agreement between the sponsor and the investigator.

Participants in Part 1 will receive a single dose in the study; therefore, after an individual participant has received a dose of IMP, withdrawal of that participant from further dosing is not possible. Participants will be monitored for the criteria listed below, which may require their withdrawal from some or all study procedures if continuation is not in their best interests, except when the withdrawal is a result of withdrawal of consent.

Participants in Parts 2 and 3 will be withdrawn from the study drug for the following reasons:

- Experiencing a serious or severe AE including but not limited to:
  - corrected QT interval by Fridericia's formula (QTcF) of >500 msec or increase in QTcF of >60 msec from baseline (confirmed following a repeat ECG)
  - alanine aminotransferase (ALT) concentration >3 × the upper limit of the reference range (confirmed following a repeat ALT blood test)
- Pregnancy (see [Section 9.5](#))
- Termination of the study
- Upon the participant's request (withdrawal of consent)
- Significant deviation from the protocol
- Concurrent illness that would adversely affect participant safety or data integrity or requirement for prohibited medication
- At the discretion of the investigator

For the purpose of withdrawal criteria, baseline will be considered as the last available assessment prior to first dose.

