#### **14.5.2 Urinalysis**

Urinalysis will be performed on-site using a dipstick according to the time schedules presented in [Appendix 2](#), [Appendix 3](#) and [Appendix 4](#).

Urine samples will be collected and processed as detailed in the CSPM.

In Part 1, any urine used for urinalysis will be added back to the full sample for PK and metabolite identification analysis. If microscopy is required, a urine sample (approximately 20 mL) will be taken from the urine PK and metabolite collection, and sent to The Doctor's Laboratory, after the void has been weighed.

In Parts 2 and 3, if microscopy is required, a urine sample will be sent to The Doctor's Laboratory.

The acceptable deviations from the nominal urine sampling time points for urinalysis are:

- On Day 3 (Part 3 only): the pre-dose urine sample will be taken  $\leq$  1 h before dosing.
- Post-dose urine samples will be taken  $\pm$  2 h from the nominal urine sampling time
- End of Study urine samples will be taken  $\pm$  1 day from the nominal urine sampling time

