**14.6 Vital Signs Measurements**

Blood pressure and heart rate will be measured by an automated recorder after the participant has been in a supine position for a minimum of 5 min and oral temperature and respiratory rate will be measured according to the time schedules presented in [Appendix 2](#)[Appendix 5](#), [Appendix 6](#) and [Appendix 7](#).

Blood pressure and heart rate orthostatic measurements will also be taken according to the time schedules presented in [Appendix 5](#), [Appendix 6](#) and [Appendix 7](#). Two measurements will be recorded; 1 supine and 1 standing. The first supine measurement will be performed after the participant has rested in a supine position for at least 5 min. The second blood pressure and heart rate measurements will be performed after the participant has been standing for at least 3 min but no more than 5 min. Orthostatic hypotension will be defined as either:

- A decrease of SBP  $\geq$  20 mmHg after 3 min standing, or
- A decrease of DBP  $\geq$  10 mmHg after 3min standing

The acceptable deviations from the nominal vital signs measurement time points are:

- Day 1 in all parts and Day 8 in Part 2: The pre-dose vital signs measurements will be taken  $\leq$  2 h before dosing
- On Days 2 and 3 (Part 3 only): the pre-dose vital signs measurements will be taken  $\leq$  1 h before dosing.
- Post-dose vital signs measurements will be taken  $\pm$  15 min from the nominal post-dose time point.
- For return visits, vital signs measurements will be taken  $\pm$  2 h from the nominal return visit time point.
- End of study visit vital signs measurements will be taken  $\pm$  1 day from the nominal time point.

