## Sponsor/Quotient Sciences Confidential

## Appendix 4 Schedule of Assessments: Part 3 (Cohorts 3A to 3C)

Study Day	Screening	Admission	Resident In-clinic							Return Visit b	End of Study Visit b
	-28 to -2	-1	1	2	3	4	5	6	7 a		
General Assessments											
Informed Consent	X										
Medical History	X	X c									
Weight, Height and BMI	X	X d								X d	X d
Vein Assessment	X										
Carbon Monoxide Breath Test	X	X									
Drug Screen	X	X									
Alcohol Breath Test	X	X									
SARS-CoV-2 Antigen e	X	X									
Randomisation f			X								
IMP Administration g			X	X	X						
Safety Assessments											
BDI-II Questionnaire	X	X									
Physical Examination	X	X									
Targeted (symptom driven) Physical Examination h			X	X	X	X	X	X	X	X	X
Safety Labs i	X	X			X		X		X	X	X
Urinalysis i	X	X			X		X		X	X	X
Follicle-stimulating Hormone (FSH) Test j	X										
Serum Pregnancy Test k	X										
Urine Pregnancy Test k		X								X	X
Single 12-Lead ECGs l	X	X	X		X	X					
TriPLICATE 12-Lead ECGs l				X		X	X	X	X		
Holter Periods m			X	X	X	X					
Vital Signs n	X	X	X	X	X	X	X	X	X	X	X
Orthostatic Vital Signs n	X		X	X	X	X				X	
Adverse Events	<-----X----->										
Prior and Concomitant Medication	<-----X----->										
PK/Pharmacogenetic Assessments											
Plasma Samples for MMV367 o			X	X	X	X	X	X	X	X	

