## Sponsor/Quotient Sciences Confidential

## Appendix 3 Schedule of Assessments: Part 3 (Cohorts 3A to 3C)

Study Day	Screening	Admission	Resident In-clinic							Return Visit b	End of Study Visit b
	-28 to -2	-1	1	2	3	4	5	6	7 a		
General Assessments											
Informed Consent	X										
Medical History	X	X c									
Weight, Height and BMI	X	X d								X d	X d
Vein Assessment	X										
Carbon Monoxide Breath Test	X	X									
Drug Screen	X	X									
Alcohol Breath Test	X	X									
SARS-CoV-2 Antigen e	X	X									
Randomisation f			X								
IMP Administration g			X	X	X						
Safety Assessments											
BDI-II Questionnaire	X	X									
Physical Examination	X	X									
Targeted (symptom driven) Physical Examination h			X	X	X	X	X	X	X		X
Safety Labs i	X	X			X	X	X	X	X	X	X
Urinalysis i	X	X			X	X	X	X	X	X	X
Follicle-stimulating Hormone (FSH) Test j	X										
Serum Pregnancy Test k	X										
Urine Pregnancy Test k		X								X	X
Single 12-Lead ECGs l	X	X	X		X	X					X
Triple 12-Lead ECGs l				X	X	X	X	X	X		
Holter Periods m			X	X	X	X					
Vital Signs n	X	X	X	X	X	X	X	X	X	X	X
Orthostatic Vital Signs n	X		X	X	X	X				X	
Adverse Events	< -----X----->										
Prior and Concomitant Medication	< -----X----->										
PK/Pharmacogenetic Assessments											
Plasma Samples for MMV367 o			X	X	X	X	X	X	X	X	
Blood Sample for CYP/UGT polymorphism p			X								

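### On scheduled bloods, Part 3 has no post-dose chemistry until just before the last dose, so the confirmed-ALT withdrawal rule cannot act before dose 2 and is unlikely to act before dose 3

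*Protocol*

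**What the plan says.** - **Dosing.** Protocol 8.1.3 gives one dose on each of Days 1, 2 and 3. Section 11.2 lets doses 2 and 3 move by 30 min either way around the time set by the Day 1 dose.
- **Withdrawal rule.** Section 8.3: "Participants in Parts 2 and 3 will be withdrawn from the study drug for the following reasons". The list opens with serious or severe adverse events and gives two numeric examples, one on QTcF and one on ALT above 3 times the upper limit, "confirmed following a repeat ALT blood test". Investigator discretion is also on the list.
- **Schedule.** Protocol Appendix 4 places Part 3 safety bloods at screening, Day -1 and Days 3, 5, 7, 9 and 17. In Appendix 7 the safety-laboratory column is empty on Days 1 and 2. Its first entry is in the Day 3 pre-dose (-0.5 h) row, marked as the 48 h sample from Day 1. SAP Appendices 3 and 6 put the first post-dose entry in the same place. (The SAP Appendix 3 row shows extra entries after Day 3, possibly from text extraction; they do not bear on this point.)
- **Window.** Section 14.5.1: "Post-dose/post-first dose blood samples will be taken" within 1 h either side of nominal. The only other blood window there is for the end-of-study visit. Other assessments due before the same dose have a one-sided limit of 1 h or less before dosing: urine in 14.5.2 ("On Day 3 (Part 3 only): the pre-dose urine sample will be taken"), vital signs in 14.6 ("On Days 2 and 3 (Part 3 only): the pre-dose vital signs measurements will be taken") and ECGs in 14.7.
- **Review.** Section 14.5 says a physician reviews results and that they are "acted upon before the participant is dosed or receives their next dose, or is released from the study, as is appropriate".

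**The concern.** A rule that withdraws a participant from drug is useful only if its measurement arrives while there is still a dose to withhold. Of the two numeric triggers in 8.3, QTcF meets that test: Part 3 schedules ECGs before doses 2 and 3. ALT does not. Parts 1 and 2 both schedule safety bloods 24 h after the first dose. Part 3, where a 24 h result could still stop a later dose, has none.

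What is at stake is narrow. A participant whose ALT crossed the threshold after dose 1 or dose 2, without symptoms that would prompt an extra sample, would probably receive all the remaining doses before the rule could be applied. No analysis or conclusion of the trial is affected.

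**Working it through.** The documents state no figure to reproduce. The check is interval arithmetic in hours after the first dose.

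**Inputs.** Dose 2 is at 24 ± 0.5 h and dose 3 at 48 ± 0.5 h (8.1.3, 11.2). The first safety blood is nominally at 47.5 h (the -0.5 h row heading) or 48 h (the label in that row), ± 1 h (Appendix 7, 14.5.1).

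**1. Before dose 2.** The earliest compliant sample is at 47.5 − 1 = 46.5 h. The latest compliant dose 2 is at 24.5 h. The sample therefore comes at least 46.5 − 24.5 = 22 h after dose 2, and no scheduled post-dose result can exist when dose 2 is given. Two of the three doses precede any scheduled post-dose blood.

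**2. Before dose 3.**

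| Reading of nominal time | Window (h) | Largest lead, dose on time | Largest lead, dose 30 min late | Largest overrun, dose on time |
|---|---|---|---|---|
| 47.5 h after dose 1 | 46.5 to 48.5 | 48 − 46.5 = 1.5 h | 48.5 − 46.5 = 2.0 h | 48.5 − 48 = 0.5 h |
| 48 h after dose 1 | 47 to 49 | 48 − 47 = 1.0 h | 48.5 − 47 = 1.5 h | 49 − 48 = 1.0 h |

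Taken exactly at nominal, the lead is 0 to 0.5 h. Section 10.3.2 times safety assessments from the start of dosing. If that means the Day 3 dose for this row, the sample moves with the dose: the lead is at most 1.5 h and the overrun at most 0.5 h. The 2 h lead arises only if the clock runs from dose 1 and dose 3 is late.

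**3. What must fit.** Confirmation needs a first draw, its result, a second draw and its result. Even 2 h allows 1 h per draw and result on average. The bloods go to a central laboratory (15.2), and its turnaround is not given.

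**4. With a Day 2 pre-dose sample.** Take it before dose 2, between 23.5 − 1 = 22.5 h and 24.5 h. The lead to dose 3 runs from 47.5 − 24.5 = 23 h to 48.5 − 22.5 = 26 h.

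**5. Part 1 cover for the proposed regimen.** The total dose is 3 × 200 = 600 mg, and 600/750 = 80% of the planned Cohort 1C dose. Predicted AUC(0-inf) in Table 2 is 112 against 127 µg.h/mL, or 88% (90% with the 114 given in the Section 6.2 text).

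**6. Blood volume.** Appendix 7 has 30 PK samples (10 + 4 + 10 + 2 + 4). Safety bloods rise from 7 to 8, and there is 1 genetic sample: 39 in all. The 550 mL limit (10.3.1) is reached at a mean of 550/39 = 14.1 mL. Allowing a 0.5 mL cannula discard for each, it is (550 − 19.5)/39 = 13.6 mL. Sample volumes are not stated.

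**The case against.** The case for leaving the schedule alone is substantial. The ALT item is only an example within a wider list, and 8.3 also allows withdrawal at the investigator's discretion, so a single unconfirmed result can stop dosing. Section 14.13 permits extra safety bloods at any time. The SAC may change safety time points (8.2.1). Part 1 takes bloods at 24, 96 and 144 h before Part 3 begins, and 8.2.2 caps the total Part 3 dose and predicted exposure at levels already evaluated there. The main group waits for sentinel safety data to 96 h after the final dose. Section 6.4.1 lists gastrointestinal, cardiovascular and respiratory risks and no hepatic one. The 30 min dosing tolerance does not stop anyone from holding a dose for safety, and a fast laboratory might confirm an ALT in time.

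Most of this stands, and it keeps the point modest. Three limits remain. An unscheduled sample needs a prompt, and an ALT rise without symptoms gives none. Part 1 covers total dose and exposure but not repeat dosing. The sentinel gate protects later participants; the active sentinel has had all three doses before it applies.

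A reader might infer that Section 14.5 is breached. It is not: its wording covers action before the next dose or before release, as appropriate. A reader might also infer that the Day 3 bloods should carry the same 1 h limit as urine, vital signs and ECGs. That would shorten the longest available lead, which is already too short.

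**Conclusion.** The point holds for scheduled bloods. That the rule cannot act before dose 2 follows directly from the schedule. That it is unlikely to act before dose 3 is an inference: it rests on a lead of 0 to 0.5 h nominally and at most 1 to 1.5 h for an on-time dose, and on the assumption that two central-laboratory results will not usually be back in that time. The committed cohort is 8 participants (6 active), with up to 24 (18 active) if Cohorts 3B and 3C run.

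This is a worthwhile and cheap safety improvement, not a defect that makes Part 3 unsafe. Two stronger readings go beyond the documents. One is that participants have no ALT protection during dosing; discretion and unscheduled bloods remain. The other is that the two-sided window contaminates a baseline; SAP 11.4.1 sets the laboratory baseline at admission on Day -1, so the window only makes the pre-dose label on the Day 3 sample unreliable.

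**What to change.** **Main change.** Add a Day 2 pre-dose (24 h) chemistry sample including ALT to the PK draw already scheduled then, and require its review before the Day 3 dose. Keep the Day 3 sample, which is the only scheduled chemistry between doses 2 and 3. Update protocol Appendices 4 and 7 and SAP Appendices 3 and 6 to match.

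**Minor tidy-up.** In 14.5.1, state that the Part 3 Day 2 and Day 3 pre-dose safety bloods are taken before dosing, with no 1 h cap.

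**Cost.** One extra tube and panel per participant and one more result to review. There is no extra venepuncture or visit, since participants are resident and already fasted for dosing. The added volume should fit within 550 mL, subject to the unstated tube sizes. Dose 2 would still be given without a post-dose result.

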#### **14.5.2 Urinalysis**

Urinalysis will be performed on-site using a dipstick according to the time schedules presented in [Appendix 2](#), [Appendix 3](#) and [Appendix 4](#).

Urine samples will be collected and processed as detailed in the CSPM.

In Part 1, any urine used for urinalysis will be added back to the full sample for PK and metabolite identification analysis. If microscopy is required, a urine sample (approximately 20 mL) will be taken from the urine PK and metabolite collection, and sent to The Doctor's Laboratory, after the void has been weighed.

In Parts 2 and 3, if microscopy is required, a urine sample will be sent to The Doctor's Laboratory.

The acceptable deviations from the nominal urine sampling time points for urinalysis are:

- On Day 3 (Part 3 only): the pre-dose urine sample will be taken  $\leq$  1 h before dosing.
- Post-dose urine samples will be taken  $\pm$  2 h from the nominal urine sampling time
- End of Study urine samples will be taken  $\pm$  1 day from the nominal urine sampling time

#### **14.5.3 Pregnancy Test**

Serum and urine highly sensitive pregnancy tests will be performed as detailed in [Appendix 2](#), [Appendix 3](#) and [Appendix 4](#). The samples will be collected and processed as detailed in the CSPM.

**Sponsor/Quotient Sciences Confidential**

---

**14.5.4 Follicle-Stimulating Hormone Test**

Serum FSH tests will be performed as detailed in [Appendix 2](#), [Appendix 3](#) and [Appendix 4](#). The samples will be collected and processed as detailed in the CSPM.

**14.5.5 Drug Screen**

A urine drug screen will be performed on-site using a point of care testing method (e.g. Alere Drug Screen Test Cup) according to the time schedules presented in [Appendix 2](#), [Appendix 3](#) and [Appendix 4](#). The sample will be collected and processed as detailed in the CSPM. Participants will be screened for the drugs of abuse listed in [Appendix 1](#).

**14.5.6 Alcohol Breath Test**

An alcohol breath test will be performed according to the time schedules presented in [Appendix 2](#), [Appendix 3](#) and [Appendix 4](#). A positive result will exclude the participant from dosing.

**14.5.7 Carbon Monoxide Breath Test**

A carbon monoxide breath test will be performed according to the time schedules presented in [Appendix 2](#), [Appendix 3](#) and [Appendix 4](#). A result of greater than 10 ppm will exclude the participant from the study.

**14.5.8 SARS-CoV-2 Tests**

Testing for the SARS-CoV-2 virus will be performed at screening and admission and may be performed at other time points, if required, based on current infection rates and availability of tests. Tests will be performed according to the time schedules presented in [Appendix 2](#), [Appendix 3](#) and [Appendix 4](#). The samples will be collected and processed as detailed in the Screening Sample Processing Manual and CSPM.

Testing time points may be changed and additional time points may be added throughout the study as required. The decision on COVID-19 testing and the definition of the testing time points are subject to change based on the current risk mitigation in place and will be agreed by the study team and documented in the ISF via the Clinical Kick-Off Meeting minutes.

**14.5.9 Genetic Samples**

In Part 1, Part 2 (Period 1 only) and Part 3, one mandatory blood sample per participant will be collected on Day 1 prior to IMP administration ( $\leq 2$  h before dosing) to investigate allelic variants related to drug metabolism cytochrome P450 (CYP) enzymes and drug transporters that are potentially involved in the MMV367 absorption, distribution, metabolism and excretion. The blood sample and the extracted DNA will be kept until the end of study and will only be analysed under specific circumstances, including abnormal or unexpected PK or safety results. The decision to conduct the analysis will be taken once all data is available after last participant visit. The blood sample and extracted DNA will be destroyed either upon completion of analysis or when it is confirmed that they will not be required for analysis.

The sample will be collected and processed as detailed in the CSPM.

